4.2 Timing of interim analyses and design adaptations

Not Applicable

4.3 Definition of end of study

Completion of this study as a whole will occur upon the availability of the last data point.

4.4 Early study termination

The study can be terminated at any time for any reason due to an unavoidable event by Novartis. Should this be necessary, the patient should be seen as soon as possible and the same assessments should be performed as described in Section 7 for a discontinued or withdrawn patient. The investigator may be informed of additional procedures to be followed in order to ensure that adequate consideration is given to the protection of the patient's interests. The investigator will be responsible for informing IRBs and/or ECs of the early termination of the trial.

5 Population

5.1 Patient population

Pediatric patients ≥ 2 years old to <6 years old with transfusional hemosiderosis that are candidates for treatment with deferasirox. Patients enrolled in this study are not permitted to participate in additional parallel investigational drug or device studies. Patients who failed screening may be re-screened with Novartis confirmation. Patients who complete the study may not be re-enrolled for a second course of treatment.

The investigator or designee must ensure that only patients who meet all the following inclusion and none of the exclusion criteria are offered treatment in the study.

5.2 Inclusion criteria

Written informed consent must be obtained prior to any screening procedures.

1. Patients ≥ 2 to <6 years old diagnosed with transfusional hemosiderosis
2. Documented history of red blood cell transfusions
3. Written informed consent/assent before any study-specific procedures. The consent will be obtained from caregiver(s) or patient's legal representative. Investigators will also obtain assent of patients according to local, regional, or national regulations.
4. For patients on prior DFX: Serum ferritin (SF) >500 ng/mL, measured at screening visit 1 and requiring a DFX daily dose equivalent to FCT ≥ 7 mg/kg/day.
5. For patients on a prior chelator other than DFX (e.g. deferiprone or deferoxamine) or chelation naive: Serum ferritin (SF) >1000 ng/mL measured at screening visits 1 and 2.

5.3 Exclusion criteria

Patients eligible for this study must not meet **any** of the following criteria:

1. Patients that receive more than one iron chelator at the same time as current iron chelation treatment. (Patients who have received combination therapy in their medical history but are currently being treated with a single ICT agent are eligible.)
2. Patients continuing on deferoxamine or deferiprone in addition to study treatment. (Patients switching to or continuing on deferasirox are eligible).
3. Unresolved adverse events if the patient was previously treated with deferiprone or deferoxamine or deferasirox.

4. Significant proteinuria as indicated by a urinary protein/creatinine ratio $> 0.5 \text{ mg/mg}$ in a non-first void sample urine measured at screening visit 1.
5. Serum creatinine $>$ age adjusted ULN measured at any screening visit
6. Creatinine clearance below 90 mL/minute measured at any screening visit. Creatinine clearance using the Schwartz formula will be estimated from serum creatinine measured at each respective visit.
7. ALT and/or AST $> 2.5 \times \text{ULN}$ measured at screening visit 1.
8. Total bilirubin (TBIL) $> 1.5 \times \text{ULN}$ measured at screening visit 1.
9. Patients with significant impaired GI function or GI disease that may significantly alter the absorption of oral deferasirox FCT (e.g. ulcerative diseases, uncontrolled nausea, vomiting, diarrhea, malabsorption syndrome, or small bowel resection).
10. History of and/or laboratory evidence of active Hepatitis B or Hepatitis C (HBsAg in the absence of HBsAb OR HCV Ab positive with HCV RNA positive).
11. Liver disease with severity of Child-Pugh Class B or C.
12. History of hypersensitivity to any of the study drug or excipients.
13. Patients participating in another clinical trial or receiving an investigational drug.
14. Patients with a known history of HIV seropositivity.
15. Patients unwilling or unable to comply with the protocol.
16. History of malignancy of any organ system, treated or untreated, within the past 5 years whether or not there is evidence of local recurrence or metastases, with the exception of localized basal cell carcinoma of the skin.
17. Significant medical condition interfering with the ability to partake in this study (e.g. uncontrolled hypertension, unstable cardiac disease not controlled by standard medical therapy, systemic disease: cardiovascular, renal, hepatic, etc.).
18. Female patients who reach menarche and they or their caregivers refuse pregnancy testing and/or if there is a positive pregnancy test result.

6 Treatment

6.1 Study treatment

The investigational study drug for this trial is crushed deferasirox (ICL670) FCT for oral use. Deferasirox FCT dosing is based on subject's weight, outlined below in [Table 6-1](#).

To guide the investigator and/or pharmacist/designee on the number of deferasirox FCT tablets of a given strength to prescribe/dispense to a given subject, taking into account the subject's body weight and protocol specified dosing scheme, a dosing table ([Table 6-1](#)) has been provided.

For each patient the investigator, pharmacist and/ or designee will calculate a target daily dose taking into account patient's body weight. When the exact calculated dose cannot be reached with the deferasirox FCT strengths available, the closest daily dose available will be prescribed and dispensed. The following dosing [Table 6-1](#) provides an efficient combination of FCT strengths reaching a certain daily dose for each body weight range.

Example illustrating this approach is provided below:

For a patient with a body weight of 20 kg and a deferasirox FCT dose of 14 mg/kg/day, the calculated daily dose is 280 mg. Taking into account the available deferasirox FCT strengths of 90, 180 and 360 mg, the closest daily dose the patient can receive is 270 mg, by taking 2 crushed FCT tablets: 1 x 90 mg + 1 x 180 mg. This combination can be found in the # of Tablets to dispense column to the far right in Table 6-1, for patients receiving 14 mg/kg/day of deferasirox FCT with a body weight between 17-22 kg.

Table 6-1 Deferasirox FCT Weight Dosing Table

3.5 mg/kg/ day [kg]	7 mg/kg/ day [kg]	10.5 mg/kg/ day [kg]	14 mg/kg/ day [kg]	17.5 mg/kg/ day [kg]	21 mg/kg/ day [kg]	24.5 mg/kg/ day [kg]	28 mg/kg/ day [kg]	# of Tablets to dispense		
								90 mg	180 mg	360 mg
19-38	10-19	7-12	5-9	5-7	5-6	5		1		
39-64	20-32	13-21	10-16	8-12	7-10	6-9	5-8		1	
	33-45	22-30	17-22	13-18	11-15	10-12	9-11	1	1	
	46-57	31-38	23-28	19-23	16-19	13-16	12-14			1
	39-47	29-35	24-28	20-23	17-20	15-17		1		1
	48-55	36-41	29-33	24-27	21-23	18-20			1	1
		42-48	34-38	28-32	24-27	21-24		1	1	1
		49-54	39-43	33-36	28-31	25-27			2	
			44-48	37-40	32-34	28-30		1		2
			49-54	41-45	35-38	31-33			1	2
				46-49	39-42	34-36		1	1	2
				50-53	43-45	37-40				3
					46-49	41-43		1		3
					50-53	44-46			1	3
						47-49		1	1	3
						50-52				4

These dosing tables have been constructed for each dosing group considering lower (5th) and upper (98th) percentiles from weight charts for children aged ≥ 2 to < 6 years. This is taking into account that the study will enroll male or female children, ≥ 2 and < 6 years. For patients with a low body weight and lower daily DFX dosing requirements (e.g. below 19 kg body weight in the 3.5 mg/kg/day dosing group) the needs will not allow for the use of the smallest tablet strength available. In such cases a written request will be sent to Novartis, to advise on the individual patient enrolment / dose adjustments options.

The patient will be dispensed deferasirox FCT in accordance with the protocol. For patients already well-managed on prior treatment with deferoxamine or deferasirox DT, a starting dose of crushed deferasirox FCT is outlined below in [Table 6-2](#).

Table 6-2 Equivalent dose of deferasirox FCT

ICT Dose Prior to Enrollment	Starting Dose		
	Deferoxamine (mg/kg/day)	Deferasirox DT (mg/kg/day)	Deferasirox FCT (mg/kg/day)
10	5	3.5	
20	10	7	
30	15	10.5	
40	20	14	
50	25	17.5	

Dose equivalence between deferiprone and deferasirox has not been established in clinical studies. For patients pre-treated with deferiprone, the starting dose of deferasirox FCT should be 14mg/kg/day.

Safety assessment will be performed weekly after treatment initiation and thereafter monthly during the study. Monthly serum ferritin values and trends will be used to adapt the treatment of the patients together with safety data.

Patients will continue therapy for 24 weeks.

6.1.1 Dosing regimen

The recommendations for deferasirox FCT daily dose for pediatric patients' age ≥ 2 to <6 years with transfusional iron overload are the same as for adult patients, i.e. based on the weight of the patient. Changes in weight of pediatric patients over time must be taken into account when calculating the dose.

In children with transfusional iron overload aged between 2 and 5 years, exposure is lower than in adults. This age group may, therefore, require higher doses than are necessary in adults. However, the initial dose should be the same as in adults, with close monitoring by the investigator, followed by individual titration.

Table 6-3 Dose and treatment schedule

Study treatments	Pharmaceutical form and route of administration	Dose	Frequency and/or Regimen
Crushed Deferasirox FCT	Film-coated tablets p.o	Minimum dose 3.5 mg/kg/day Targeted starting dose 14 mg/kg/day Maximum dose 28 mg/kg/day Dosage is ascertained by patient weight. Please refer to dose weight Table 6-1 for the recommended dose in mg/ kg/day	Once daily; all doses must be crushed prior to administration

Deferasirox FCT is for oral use. The full daily dose of one or more film-coated tablets must be crushed in the home environment and administered by sprinkling the full dose on to soft food (e.g., yogurt or apple sauce [pureed apple]). The dose must be immediately and completely consumed, and not stored for future use. The study medication should be taken once daily, preferably at the same time each day.

Subjects who have been established on other chelation therapy will perform a 5 day wash-out from the former medication details are provided in [Section 7.1.2](#).

The patient's daily dose will be rounded to the nearest whole tablet according to the available strengths of deferasirox FCT tablets (90 mg, 180 mg, and 360 mg). The appropriate daily dose will be calculated by the investigator based on the patient's actual body weight see [Table 6-1](#).

The investigator and/or designee will instruct the caregiver and patient to crush the study drug and then take the full daily dose of one or more film-coated as prescribed. Examples among others of an adequate method of crushing of the FCT may be between two pieces of wax paper with a rolling pin or with a commercially available pill crusher. All doses planned and prescribed to the patient, and all dose changes including reasons for change during the study must be recorded in the case report form(CRF).

During regular study visits, the investigator or pharmacist will give to the patient the appropriate number of deferasirox tablets based on the patient's calculated dose. The number of tablets of each strength of deferasirox dispensed will be recorded in the study site's Study Drug Log.

Patients will be obliged to return all unused study medication at their next visit. Study medication returned by the patients will be counted and unused study medication will be recorded by the investigator/pharmacist/designee involved in the study.

Drug accountability will be noted by the field monitor during site visits and at the completion of the trial.

6.1.2 Ancillary treatments

Not Applicable

6.1.3 Rescue medication

Not Applicable

6.1.4 Guidelines for continuation of treatment

For patients who are unable to tolerate the protocol-specified dosing schedule, dose reductions are permitted at the discretion of the investigator in order to keep the patient on study drug. These changes must be recorded on the dosage administration record electronic (e)CRF.

The majority of dose reductions, modifications, interruptions are covered in [Section 6.3](#) and with further details in [Table 6-4](#). For all cases where a dose adjustment is considered necessary, but is not covered in the following sections, the investigator will send a written request to Novartis. The request must justify the dose change and provide all supportive clinical and laboratory information for complete evaluation by Novartis. Any dose adjustment for reasons not included in this section needs to be authorized by Novartis. A written reply will be promptly sent back to the investigator by Novartis.

6.1.5 Treatment duration

The planned duration of treatment is 24 weeks. Patients may be discontinued from treatment with the study drug earlier due to unacceptable toxicity or at the discretion of the investigator or the patient. Premature patient withdrawal refers to the point/time when the patient exits from the study prior to planned completion of all study treatment administration and/or

assessments. At this time, all study treatment is discontinued and after the 30-day safety follow-up (as possible), no further assessments are planned.

Patients may continue or resume prescribed iron chelation therapy as per investigator discretion.

6.2 Dose escalation guidelines

ICL670F2429 not being an early development study, dose escalation guidelines do not apply; for information on dosing regimen, please refer to section 6.1 of the protocol.

6.2.1 Starting dose rationale

Not applicable

6.2.2 Provisional dose levels

Not Applicable

6.2.2.1 Implementation of dose escalation decisions

Not Applicable

6.2.2.2 Intra-Patient dose escalation

Not Applicable

6.2.3 Definitions of dose limiting toxicities (DLTs)

Not Applicable

6.3 Dose modifications

6.3.1 Dose modification and dose delay

For patients who do not tolerate the protocol-specified dosing schedule, dose interruptions and/or reductions are either recommended or mandated in order to allow patients to continue the study treatment.

These dose modifications are summarized in [Table 6-4](#). Deviations to mandatory dose interruptions and/or reductions are not allowed. Permanent treatment discontinuation is mandatory for specific events indicated as such in [Table 6-4](#) or listed in [Section 7.1.5](#).

These dose changes must be recorded on the Dosage Administration Record CRF.

6.3.1.1 Change in patient's weight

The dose of study medication is to be adapted as per locally approved prescribing information during the study if the change (increase or decrease) in body weight exceeds 10% of the body weight compared to baseline or the last dose adjustment due to change in patient's body weight.

6.3.1.2 Elevations in serum creatinine

Serum creatinine must be monitored during the study as stated in visit schedule, refer to [Table 7-1](#).

For pediatric patients the following dose adjustment guidance applies:

- At single increase in serum creatinine (SCr) $>\text{ULN}$ and increased by $\geq 33\%$ from baseline, maintain DFX dose level and repeat the assessment at next visit as clinically indicated.
- If serum creatinine (SCr) $>\text{ULN}$ and increased by $\geq 33\%$ from baseline on 2 consecutive visits, deferasirox dose reduction by 7 mg/kg/day for the FCT is required.
- If after dose reduction, resolution of serum creatinine occurs ($<33\%$) and within normal limits, dose can be re-escalated to 100% of the last dose.

If increase in serum creatinine recurs again within 2 months according to guidelines above, therapy needs to be reduced to 50% of the last dose.

After 2 months, if the serum creatinine increase does not recur, study medication may be re-escalated to 100% of the last dose depending on the clinical judgement of the investigator.

If after an initial dose reduction, a progressive increase in serum creatinine beyond the ULN is observed, or SCr increase recurs, repeat at adequate dose, a treatment interruption is recommended.

After a treatment interruption, if serum creatinine falls below the age-appropriate ULN on two consecutive visits, it is recommended to resume therapy at 50% of the last dose, and after 1 month, if the serum creatinine increase does not recur, study medication can be returned to

100% of the last dose (including body weight adjustment if required) depending on the clinical judgement of the investigator.

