Single serum creatinine increase $\geq 33\%$ above baseline value and $> \text{ULN}$	
Deferasirox dose reduction by 7 mg/kg/day for the FCT is necessary.
 
If after dose reduction, resolution of serum creatinine occurs (<33%) and within normal limits, dose can be re-escalated to 100% of the last dose.
 
If increase in serum creatinine recurs again within 2 months according to guidelines above, therapy needs to be reduced to 50% of the last dose
 
After 2 months, if the serum creatinine increase does not recur, study medication may be re-escalated to 100% of the last dose depending on the clinical judgement of the investigator.
 
If after an initial dose reduction, a progressive increase in serum creatinine beyond the ULN is observed, or SCr increases re-occur repeatedly at adequate dose, a treatment interruption is recommended.
 
After a treatment interruption, if serum creatinine falls below the age-appropriate ULN on two consecutive visits, it is recommended to resume therapy at 50% of the last dose, and after 1 month, if the serum creatinine increase does not recur, study medication can be returned to 100% of the last dose (including body weight adjustment if required) depending on the clinical judgement of the investigator.

Patients who met the eligibility criteria and who experience a renal function decrease $< \text{LLN}$ ($\text{CrCl} < 90 \text{ml/min}$) at 2 consecutive visits	
If decrease cannot be attributed to other causes, DFX must be dose reduced by 7mg/kg/day.
 
If after dose reduction the renal function increases $>$

Recommended dose modifications for deferasirox

LLN (CrCl >90ml/min), dose may be re-escalated to the last daily dose prior dose reduction depending on the clinical judgement of the investigator.
If after dose reduction the renal function remains <LLN (CrCl <90ml/min), treatment must be interrupted.
Treatment may be reinitiated depending on the clinical judgement of the investigator.
If creatinine clearance falls below 60ml/min study treatment must be discontinued.

Investigations (Hepatic)**Isolated direct (conjugated) Bilirubin elevation**

> ULN – 1.5 x ULN

Maintain dose level

> 1.5 - 3.0 x ULN

Omit dose with weekly monitoring of LFTs, or more frequently if clinically indicated, until resolved to \leq 1.5 x ULN.

If resolved in \leq 14 days, then maintain dose level

If resolved in > 14 days, then dose reduction of 3.5 or 7 mg/kg/day for deferasirox FCT.

> 3.0 - 10.0 x ULN

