8.1 Adverse events

8.1.1 Definitions and reporting

An adverse event is defined as the appearance of (or worsening of any pre-existing) undesirable sign(s), symptom(s), or medical condition(s) that occur after patient's signed informed consent has been obtained.

Abnormal laboratory values or test results occurring after informed consent constitute adverse events only if they induce clinical signs or symptoms, are considered clinically significant, require therapy (e.g., hematologic abnormality that requires transfusion or hematological stem cell support), or require changes in study medication(s).

Adverse events that begin or worsen after informed consent should be recorded in the Adverse Events CRF. Conditions that were already present at the time of informed consent should be recorded in the Medical History page of the patient's CRF. Adverse event monitoring should be continued for at least 30 days following the last dose of study treatment. Adverse events (including lab abnormalities that constitute AEs) should be described using a diagnosis

whenever possible, rather than individual underlying signs and symptoms. When a clear diagnosis cannot be identified, each sign or symptom should be reported as a separate Adverse Event.

Adverse events will be assessed according to severity: mild, moderate or severe. Information about any deaths (related to an Adverse Event or not) will also be collected through a Death form.

The occurrence of adverse events should be sought by non-directive questioning of the patient (subject) during the screening process after signing informed consent and at each visit during the study. Adverse events also may be detected when they are volunteered by the patient (subject) during the screening process or between visits, or through physical examination, laboratory test, or other assessments. As far as possible, each adverse event should be evaluated to determine:

1. Severity (Mild, moderate or severe)
2. Its duration (Start and end dates)
3. Its relationship to the study treatment (Reasonable possibility that AE is related: No, Yes)
4. Action taken with respect to study or investigational treatment (none, dose adjusted, temporarily interrupted, permanently discontinued, unknown, not applicable)
5. Whether medication or therapy was given (no concomitant medication/non-drug therapy, concomitant medication/non-drug therapy)

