8.1.2 Laboratory test abnormalities

8.1.2.1 Definitions and reporting

Laboratory abnormalities that constitute an Adverse event in their own right (are considered clinically significant, induce clinical signs or symptoms, require concomitant therapy or require changes in study treatment), should be recorded on the Adverse Events CRF. Whenever possible, a diagnosis, rather than a symptom should be provided (e.g. anemia instead of low

hemoglobin). Laboratory abnormalities that meet the criteria for Adverse Events should be followed until they have returned to normal or an adequate explanation of the abnormality is found. When an abnormal laboratory or test result corresponds to a sign/symptom of an already reported adverse event, it is not necessary to separately record the lab/test result as an additional event.

Laboratory abnormalities, that do not meet the definition of an adverse event, should not be reported as adverse events. A severe event does not automatically indicate a SAE unless it meets the definition of serious as defined below and/or as per investigator's discretion. A dose hold or medication for the lab abnormality may be required by the protocol in which case the lab abnormality would still, by definition, be an adverse event and must be reported as such.

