2.11.1 Adverse events (AEs)

All AEs recorded during the study are coded using the latest version of the medical dictionary for regulatory activities (MedDRA). Adverse events will not be assessed according to the common terminology criteria for AEs (CTCAE); instead, AE severity (mild, moderate, severe) will be used to report treatment-emergent AEs starting on or after the date of first study medication (including AEs that start within 30 days after the discontinuation of the study medication).

Frequency tables for treatment-emergent AEs will be presented. The summary tables will include the number of patients, and the percentage of patients experiencing the AE. Multiple occurrences of the same event in the same patient will be counted only once in the frequency tables. However, all adverse events will be included in the AE listings.

Frequency tables will display at least the MedDRA system organ class or preferred term, AE severity (mild, moderate, severe) or both, and relationship to study treatment. The following tables will be generated based on the data up-to 24 weeks including 30 days follow-up:

- Adverse events, regardless of study treatment relationship
- Adverse events, suspected to be study treatment related
- Serious adverse events, regardless of study treatment relationship
- Serious adverse events, suspected to be study treatment relationship
- Adverse events leading to study drug discontinuation, regardless of study treatment relationship
- Adverse events leading to study drug discontinuation, suspected to be study treatment relationship
- Adverse events requiring dose adjustment or interruption, regardless of study treatment relationship
- Adverse events requiring additional therapy, regardless of study treatment relationship

- Adverse events which are not serious adverse events, regardless of study treatment relationship

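### For a single creatinine rise of at least 33% above baseline and above the ULN, protocol section 6.3.1.2 keeps the dose while Table 6-4 cuts it by 7 mg/kg/day

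*Protocol*

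**What the plan says.** Protocol section 6.3.1.2 handles serum creatinine in two steps. For a single value above the ULN and increased by at least 33%, it reads "from baseline, maintain DFX dose level and repeat the assessment at next visit as clinically indicated". If the finding is present "on 2 consecutive visits, deferasirox dose reduction by 7 mg/kg/day for the FCT is required".

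Table 6-4 (printed after section 6.3.1.12) has two rows for a single rise. The first, at least 33% with no ULN condition, says to maintain the dose and repeat. The second begins "Single serum creatinine increase", adds that the value is at least 33% above baseline and above the ULN, and gives the action "Deferasirox dose reduction by 7 mg/kg/day for the FCT is necessary".

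Section 6.3.1 presents Table 6-4 as the summary of the dose modification rules and states: "Deviations to mandatory dose interruptions and/or reductions are not allowed".

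Under section 8.1.1, an abnormal laboratory value is an AE only if it meets one of several criteria: it causes signs or symptoms, is clinically significant, needs therapy, "or require changes in study medication(s". Section 8.1.2.1 gives a similar list. It adds that where the protocol calls for a dose hold or medication, "the lab abnormality would still, by definition, be an adverse event and must be reported as such".

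SAP section 2.11.1 plans a table of "Adverse events requiring dose adjustment or interruption, regardless of study treatment relationship". SAP section 2.6.4 plans a summary of dose reductions with reasons.

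**The concern.** Creatinine rises are a known effect of this drug, and the dose rule is the main protection for children aged 2 to under 6. A rule that depends on which page the site opens exposes children with the same result to different doses. Either error has a cost: an unnecessary cut in chelation after a chance value, or a delayed cut after a real rise.

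The trial exists to describe safety, so the reporting side matters too. If one text turns an isolated rise into an AE and the other does not, part of the AE count reflects site reading rather than the drug.

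**Working it through.** The plan states no figure on this point, so there is nothing to reproduce. The check sets the texts side by side and adds simple dose arithmetic.

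**Step 1. Same result, two actions.**

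| Creatinine finding | Section 6.3.1.2 | Table 6-4 |
|---|---|---|
| Single rise ≥33%, not above ULN | no rule | maintain, repeat |
| Single rise ≥33% and >ULN | maintain, repeat | reduce by 7 mg/kg/day |
| ≥33% and >ULN on 2 consecutive visits | reduce by 7 mg/kg/day | no separate row |

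The conflict is in the middle line. Reading the texts together does not remove it. The section's instruction to maintain expressly covers values above the ULN, whereas the table uses the ULN to separate maintaining from reducing. The table has no two-visit condition for serum creatinine, although it has one for creatinine clearance. Both texts are current; neither comes from the amendment summary.

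**Step 2. Dose after one such value.** Section: dose − 0. Table: dose − 7.

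- At 14 mg/kg/day (targeted starting dose, Table 6-3): 14 versus 14 − 7 = 7, a difference of 7/14 = 50%.
- At 28 mg/kg/day (maximum dose): 28 versus 28 − 7 = 21, a difference of 7/28 = 25%.

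The gap lasts until the next creatinine test. At nominal visit spacing it is 7 × 7 days = 49 mg/kg during the weekly visits of the first month, and 7 × 28 days = 196 mg/kg between later visits. An unscheduled test (section 7.1.9) would shorten it.

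**Step 3. AE status of a rise that is asymptomatic, not clinically significant and needs no therapy.**

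- Under Table 6-4 a change in study medication is required, so the section 8.1.1 criterion is met and the rise is an AE.
- Under section 6.3.1.2 no change is required and no other criterion is met, so it is not an AE.

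The weight rests on section 8.1.1 and the matching list in 8.1.2.1. The stronger sentence in 8.1.2.1 speaks of a dose hold or medication, not of a reduction.

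**Step 4. Outputs reached.** These are the overall AE tables, the table of AEs requiring dose adjustment or interruption (SAP 2.11.1) and the dose-reduction summary (SAP 2.6.4). Treatment-related AEs, a secondary endpoint, are reached where the investigator suspects a causal link. The primary endpoint counts selected GI preferred terms (SAP 2.8.1), so creatinine events do not enter it.

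**Step 5. Which trigger the documents favour.** Section 6.3.1.2 requires two visits. Section 6.3.1.3 applies the same structure to creatinine clearance: below 90 mL/min at two consecutive visits, reduce by 7 mg/kg/day. SAP Table 2-1 is similar for notable creatinine: more than 33% and above the ULN at two consecutive measurements at least 7 days apart. Only the one table row points the other way.

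**The case against.** The strongest reply is that the protocol names an outside standard. The study design entry of the protocol summary says dosing standards and adjustments follow the EU label throughout. A site could settle the matter there, and the label, not internal consistency, should decide which trigger is right. This stands as a limit on the recommendation: the label is not among the documents reviewed, so the preference for the two-visit rule is inferred from the protocol and SAP alone. It does not excuse two conflicting instructions in the document that sites work from.

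A second reply is that the table is headed as recommended modifications, section 6.3.1.2 is introduced as guidance, and section 6.3.1 says modifications are either recommended or mandated. The ban on deviations may therefore not bite. This stands in part. A site that reduces under the table does not breach a ban on departing from mandatory reductions. A site that maintains under the section breaches it only if the table row is mandatory. The row's own wording, that the reduction is necessary, suggests that it is, but the heading leaves doubt.

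A third reply is that AE status does not turn on the dose rule alone, since an investigator may judge a single rise clinically significant. That is correct, and the reporting effect is confined to rises that meet no other AE criterion.

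**Conclusion.** The point holds. For one creatinine value at least 33% above baseline and above the ULN, the protocol says both maintain and reduce by 7 mg/kg/day. The difference is 7 mg/kg/day until the next test, half the dose for a child on 14 mg/kg/day. For a rise meeting no other AE criterion, the text followed also decides whether an AE is reported. This should be corrected, but it does not undermine the trial: the primary GI endpoint definition and the sample size are untouched.

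A reader might infer more than the documents support:

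- **That the table stops chelation in a child on 7 mg/kg/day.** The sum 7 − 7 = 0 is arithmetic, not an instruction. Table 6-3 sets a minimum of 3.5 mg/kg/day, and section 6.1.4 refers uncovered adjustments to the sponsor. The same sum arises under section 6.3.1.2 once a rise is confirmed.
- **That a stated number of the 40 children will be affected.** The documents give no rate for single rises meeting both conditions. The 3.1% in section 1.2.1.2 is for two or more consecutive occasions over a 5-year study. The 36% is for mild increases, mostly within the normal range, in patients of all ages.
- **That the SAP laboratory and AE tables would conflict because of this.** They use different definitions by design. SAP Table 2-1 also differs in detail from section 6.3.1.2 (more than, rather than at least, 33%; a 7-day spacing), so aligning Table 6-4 would not make them identical.

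**What to change.** Use one trigger in both places and confirm it against the EU label.

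If the two-visit rule is confirmed, change two rows of Table 6-4:

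- Row 1: *Single increase ≥33% above baseline, with or without >ULN: maintain dose, repeat at next visit.*
- Row 2: *≥33% above baseline and >ULN on 2 consecutive visits: reduce by 7 mg/kg/day.* The re-escalation and interruption text that follows stays.

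If the sponsor intends the single-rise rule, leave the table and change section 6.3.1.2.

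Optionally, the SAP could flag each creatinine-driven reduction in the dosing listing as following a single or a confirmed rise, using values already collected. This would help in reading data gathered under both texts, but the correction does not depend on it.

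The cost is two table cells (or the matching bullets in 6.3.1.2) in a written amendment under section 12.1, with approval by the sponsor, the ethics committees and, where required, the health authorities. It can go with the next amendment. It needs no new visits, tests or CRF fields.
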